Our hypothesis is that micro-dosing with a binary mixture of [¹⁴C]-BaP and another PAH will result in no change in plasma and urine [¹⁴C]-BaP metabolites, the [¹⁴C]-BaP Cmax in blood or the rate of elimination. This hypothesis will be tested by micro-dosing individuals with a binary mixture of [¹⁴C]-BaP and non-radioactive phenanthrene. We will dose individuals with 50 ng of [¹⁴C]-BaP alone and, following a washout period, previously shown to reduce [¹⁴C]-BaP levels in plasma and urine to levels below detection (<1 fg/mL), compare to a binary mixture of 50 ng [¹⁴C]-BaP and 1250 ng of non-labeled phenanthrene (non-carcinogenic PAH²), a BaP:phenanthrene ratio commonly found in food⁵. The determination of the effect of phenanthrene on uptake, metabolism and elimination of [¹⁴C]-BaP will test a basic tenet of the Relative Potency Factor (RPF) approach to risk assessment (proposed by the U.S. EPA) for PAH mixtures⁶, that there is no impact of a PAH on the pharmacokinetics of another PAH (i.e. the cumulative risk is additive).

To date, our accelerator mass spectrometry (AMS) studies with PAHs have employed a single PAH given at a single dose^{7,8}. We have chosen to employ a simple binary mixture as the simplest model to test the assumption that one PAH will not impact the kinetics of another PAH. Phenanthrene is an excellent choice as 1) it is a major component of environmental PAH mixtures^{1-5,9, 2}) it contains a bay region as does BaP and is thus metabolized in a similar fashion¹⁰, 3) it has been evaluated by IARC and EPA and considered not to be a carcinogen (IARC class 3, EPA RPF of 0)^{2,4,6} and 4) it has been previously employed safely in FDA-approved clinical trials in humans at a dose 10,000 ng¹¹. Thus, this will be the first actual test of the RPF approach to risk assessment via micro-dosing in humans of a defined binary mixture of a carcinogenic (BaP) and non-carcinogen (phenanthrene) PAH. For non-cancer risks, the EPA has set a safe lifetime **exposure** value of 40,000 ng/Kg/day⁶, a value more than 2,200 time greater than the single phenanthrene dose (1250 ng/70 Kg) proposed here.

Pharmacokinetic parameters for [14C]-BaP and metabolites, in the presence and absence of co-

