	Previously, the oral exposure slope factor for cancer risk (70 years, 70 Kg adult) for BaP using a linear, non- threshold model (EPA-IRIS) was 7.3 mg/kg-day ⁻¹ , but EPA recently lowered this to 1 mg/(kg-day) ⁴ . Cal/EPA uses a safety factor for age sensitivity (2.9 mg/kg-day ⁻¹). This risk assessment is based on high dose (1-100 mg/kg-day) exposures in rodents- 5-6 orders of magnitude higher doses than human exposures . This risk assessment may not adequately protect some populations. Studies, including our own, with PAH mixtures indicate the linear extrapolated dose may under-estimate actual human risk using the Relative Potency Factor (RPF) approach ⁶ . The RPF approach assumes linear pharmacokinetics for PAHs and their metabolites with dose but this has never been assessed in humans. With the common PAH phenanthrene, a non- carcinogenic PAH, we can test the additivity assumption of the RPF approach in the simplest (binary) mixture possible and at a ratio of the 2 PAHs present in diet.	
	Our preliminary results show the plasma level, as determined by AMS at Crew (highest concentration	

	obtained) after dosing individuals with 46 ng [¹⁴ C]-BaP, was ~ 8 fM (femto(10 ⁻¹⁵ moles/L)) ²⁰ , or 10⁷ lower than an in vitro study (50 nM) showing no adverse impact on hepatocytes. The sensitivity of AMS allows for micro-dosing with [¹⁴ C]-BaP in humans with de minimus risk to determine [¹⁴ C]-BaP and individual metabolites in the low fM range (2-20 femtograms/mL plasma). Our premise is- the best model for humans is humans. Utilizing PBPK models, we can provide a much more accurate estimate of BaP levels in human tissues following exposure at environmental levels as well as individual metabolites representing reduced or enhanced risk.			
1	Background justification should support the objectives of the research as well as the knowledge that is anticipated from the research results. Explain the need for the study and what gap in knowledge the results are expected to fill. Summarize relevant existing data, literature, past and ongoing studies, and how your study ties in with these. Provide specific methods and procedures in a later section.			
4	Is the study student-driven (for the purpose of a thesis, dissertation, or other)?		\boxtimes	
SECTION 14 - Target Enrollment		Yes	No	N/A
1	What is the target enrollment number?			
	Up to 50 people will be enrolled in this study. Our goal is for 7 subjects to complete the study.			

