0	A target enrollment number is not applicable for studies limited to chart review or review of large, pre- existing datasets, such as those originating from public health surveillance organizations.			
1	If the study is determined to be exempt, expedited, or eligible for flexibility in the application of the regulations, an approximate number is sufficient for the evaluation of risk. The PI will not be required to report enrollment numbers to the IRB over the course of the study. However, if the study involves more than minimal risk or is FDA-regulated, an exact number is required and cannot be exceeded without prior approval.			
Q	FAQ What is the "total target" enrollment number?			
2	Provide scientific justification for the target enrollment number:			
	We expect a high percentage of screen failure. If a large number of study enrollees qualify to participate in the study, we will stop enrolling subjects prior to reaching our maximum enrollment figure.			

SECTION 15 Doutising at Domographics

SECTIO	SECTION 15 - Participant Demographics		No	N/A
1	Age ranges	Check all that apply		
1a	0-7			
1b	8-17			
1c	18-89	\boxtimes		
1d	90+			
1	If the study is intended to be limited to adults, all enrolled participants must have attained the legal age to consent to research under the applicable law of the jurisdiction in which the research will be conducted. Not all states or countries consider 18 years to be the age of majority; in Oregon it is 18. Describe nuances related to participant age in the inclusion and exclusion criteria sections below. Sample recruitment or consent language : "In order to be in this study you must be of legal age to consent, which is 18 in most states."			
2	Indicate all populations permitted to enroll who may need additional safeguards or for whom additional regulations may apply:			
2a	Children		\boxtimes	
Q	Guidance on research with children			
2b	Adults lacking capacity to consent		\boxtimes	
2c	Children in foster care or wards of the state		\boxtimes	
Q	Regulations related to enrolling children in foster care or wards of the state			
2d	Pregnant women AND the study involves more than minimal risk OR a physical intervention		\boxtimes	
2e	Fetuses and/or neonates		\boxtimes	
2f	Prisoners		\boxtimes	
00	Guidance on research with prisoners. If in Oregon, submit an application to the Oregon Department of Corrections application. If outside of Oregon, contact the state DOC for instructions.			

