🛛 Data	and Safety Monitoring Plan
🗌 Depa	rtment of Corrections application
🗌 Docu	mentation that the product is an approved food additive (21 CFR 172)
🗆 Exter	nal IRB document(s)
🗆 Exter	nal study document(s)
🗆 FDA (Correspondence
🗆 FDA '	'Safe to Proceed" letter
\Box GMP	certificate or food-grade certificate that indicates that the product can be lawfully used in the US food supply
🗌 Grant	or contract if not already in Cayuse
🗆 IND c	r IDE Application for Investigational New Drug or Device
🗆 Inves	tigator brochure
🛛 Label	for investigational drug or device
🗆 Lette	r from the FDA or industry sponsor setting forth the IND number
🗆 Lette	r(s) of support or permission
🗆 Packa	ige insert
🛛 Recru	itment materials
🛛 Refer	ences or citations
□ Safet	y data if GRAS status is self-affirmed
⊠ Scree	ning or eligibility checklist(s) or document(s)
🗆 Surve	ys, questionnaires, interview or focus group guide(s)
□ Trans	lated document(s)

□ Tribal Council Resolution or other appropriate supporting documentation from the appropriate Tribal authority

Additional attachments:
🖾 Food Diary
⊠ Demographics form
Health assessment form
⊠ Cruciferous vegetable list

PI should email completed application and all relevant attachments to [contact]

Statistical Analysis Plan

Pharmcokinetic parameters were evaluated for linearity using a best fit modeling approach. First, pharmacokinetic parameters were evaluated for significant change as a functin of dose using a standard linear regression model including a fit y-intercept. Slopes were compared using a *t*-test and an alpha value of 0.05. If the parameter changed as a function of dose, we further evaluated the parameter with a linear regression model, with *k* as the slope through the origin and a Michaelis-Menten model, which assumes saturation at V_{max} and an affinity constant K, to individual parameters (p) as a function of extermal [¹⁴C]-BaP dose. The Baysesian information criterion (BIC) was used to judge the best-fit model and provide evidence of linear or saturable pharmacokinetics.

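### The SAP has no within-subject BaP-alone versus mixture contrast on any scale; when one is added, its log scale, ratio estimate and detection-limit rule should be stated

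*Combined protocol and SAP*

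**What the plan says.** The Statistical Analysis Plan is one paragraph. Parameters are to be "evaluated for significant change as a functin of dose" by "using a standard linear regression model including a fit y-intercept". Slopes are compared by a t-test at "an alpha value of 0.05". A parameter that changes with dose then goes to a second stage: a regression with k "as the slope through the origin and a Michaelis-Menten model, which assumes saturation at" V_max, with the better model chosen by BIC. The paragraph names no transformation, weighting, error model, subject term or phenanthrene term. The raw scale and constant variance are therefore the ordinary reading of the text, not something it states.

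Section 13, item 1 sets the question. The hypothesis is that adding phenanthrene "will result in no change in plasma and urine" metabolites, blood Cmax or the elimination rate. Sections 13 and 24 give 50 ng of BaP in both conditions, with 1250 ng of phenanthrene added in one. Section 20 has each subject take both. A subject who took the 50 ng dose in the earlier dose-response study within the past 12 months adds only the mixture cycle.

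On size, Section 14 says "Our goal is for 7 subjects to complete the study". Its justification deals only with recruitment ("We expect a high percentage of screen failure"). It gives no effect size, SD or power.

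**The concern.** The stated models answer a different question. They ask how a parameter moves with BaP dose, which does not vary here. The hypothesis concerns the same subject with and without phenanthrene, and the SAP gives no estimate or test for that.

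Suppose the contrast is added without a stated scale, and the SAP's untransformed approach carries over. A change in uptake or elimination is naturally a ratio R. On the raw scale a subject with level m contributes a difference of (R - 1) x m, so a subject with three times the level contributes three times the difference for the same proportional effect. On the log scale every subject contributes ln R. With 7 subjects there is little averaging to even this out.

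The direction matters because the hypothesis is one of no change. Any loss of power favours the expected answer, and Section 13 intends the results for EPA risk models. A difference in fg/mL is also harder to read as an effect on uptake or elimination than a ratio with an interval.

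**Working it through.** **Plan's own figure.** The only figure is 7 completers. Without an effect size, SD or power it cannot be reproduced. All variances and ratios below are assumptions, shown over a range.

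**Step 1: can the SAP's models be fitted?** Fourteen observations (7 subjects, 2 cycles), all at dose 50. The slope needs the sum of (dose - mean dose)², which is 14 x (50 - 50)² = 0. The design matrix [1, dose] has rank 1. No slope can be estimated, and the line through the origin cannot be told from Michaelis-Menten. Taking logs changes none of this.

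**Step 2: paired contrast, proportional error.** Simulated sets of 7 log-normal pairs (60,000 per setting), two-sided alpha 0.05, paired t-test on raw and on ln values:

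| True ratio, within-subject log SD | Scale | Between-subject log SD 0.3 | 0.5 | 0.7 |
|---|---|---|---|---|
| 1.25, 0.15 | raw | 59% | 52% | 42% |
| 1.25, 0.15 | ln | 64% | 64% | 64% |
| 1.5, 0.25 | raw | 65% | 57% | 47% |
| 1.5, 0.25 | ln | 72% | 72% | 72% |

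The loss runs from 64 - 59 = 5 points to 72 - 47 = 25 points. With no true change, the raw test rejects in 3.1-4.5% of sets and the ln test in 4.9-5.1%. The subject with the highest level holds on average 28%, 39% and 48% of the summed squared level at the three between-subject SDs, against 1/7 = 14% under equal weight.

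A separate run on CVs agrees. At ratio 1.5 and within-subject CV 20%, raw power is 0.86, 0.84, 0.77 and 0.63 at between-subject CV 20%, 30%, 50% and 80%, against about 0.89 on the log scale.

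**Step 3: pairing against scale.** At between-subject CV 50%, within-subject CV 20% and ratio 1.5, power is 0.17 unpaired raw, 0.18 unpaired log, 0.77 paired raw and 0.89 paired log. Pairing is the larger gain; the scale comes second.

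**Step 4: is proportional error safe to assume?** Section 13, item 3 puts preliminary Cmax near 8 fM after 46 ng. C20H12 (Section 24) has molecular weight 20 x 12 + 12 x 1 = 252, so 8 x 10⁻¹⁵ mol/L x 252 g/mol is about 2.0 x 10⁻¹² g/L, or 2 fg/mL. Section 13, item 1 puts the detection limit at 1 fg/mL. Cmax is thus only about twice the limit, and additive assay error is plausible.

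Take median 2 fg/mL, an assumed additive SD of 0.3 fg/mL, true ratio 1.25 and between-subject log SD 0.3, 0.5, 0.7. Raw power is 0.73, 0.69, 0.62 and log power 0.68, 0.60, 0.51, so the ranking reverses. Adding 10% proportional error brings the two within about 3 points.

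**Step 5: values below detection.** With median 2 and limit 1 fg/mL, the expected share of BaP-alone Cmax values below the limit is Φ(ln(1/2)/SD), ignoring assay error: Φ(-2.31) = 1%, Φ(-1.39) = 8% and Φ(-0.99) = 16% at between-subject log SD 0.3, 0.5 and 0.7. A log analysis needs a rule for these.

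**Step 6: what the ratio would deliver.** The 95% interval is exp(mean difference ± t x SD x √2 / √7), with t = 2.447 on 6 degrees of freedom. At within-subject log SD 0.15 the half-width is 2.447 x 0.212 / 2.646 = 0.196, a factor of 1.22 either way. At 0.25 it is 2.447 x 0.354 / 2.646 = 0.327, a factor of 1.39.

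**The case against.** The strongest reply is that the scale is a side issue. The quoted models cannot be fitted to this study at all, so power figures for a paired test describe an analysis the SAP does not contain. That stands, and it is why the missing contrast comes first here. The scale still has to be chosen when the contrast is written, and a SAP that added a paired comparison of raw values would leave the question open.

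A second reply is that proportional error is assumed. That also stands: Step 4 shows that additive error can remove or reverse the power advantage. Power alone therefore does not decide for the log scale. The case rests equally on the question being about a ratio, and on the ratio with its interval being a conventional way to report it.

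Three stronger readings are tempting, and the documents support none of them:

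- A reader might infer that the highest-exposure subject dominates and that power is lost. Even under proportional error the top subject's average share stays below half, and the loss is near 5 points at the lowest spread shown.
- A reader might take "metabolites in the low fM range (2-20 femtograms/mL plasma") as a tenfold spread between subjects. Section 13, item 3 gives it as what the assay can measure across BaP and its metabolites. No between-subject SD appears anywhere.
- A reader might extend the log scale to a regression of ln parameter on ln dose, with the slope compared with 1. There is one BaP dose here. Under linear kinetics an elimination rate constant does not depend on dose, so its expected slope is 0, and the comparison with 1 would reject linearity when it holds.

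**Conclusion.** The concern holds in a limited form. It is certain from the documents that the SAP's dose models cannot be estimated with one BaP dose, and that no within-subject BaP-alone versus mixture contrast is specified on any scale. It is conditional that raw differences would cost power: about 5 to 25 points if error is proportional and the assumed SDs apply, little or nothing if additive assay error matters as well, and a gain rather than a loss if additive error is the main source. Type I error is not inflated on either scale in the proportional-error runs. Logging alone would not repair the SAP. The scale, the estimate and the detection-limit rule should be settled together with the contrast, before the data are analysed.

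**What to change.** Add to the SAP, as the analysis of the Section 13 hypothesis:

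1. For each completer, the difference ln(mixture) - ln(BaP alone) for Cmax, metabolite amounts and elimination rate.
2. The geometric mean ratio, exp(mean difference), with its confidence interval and the level stated.
3. A rule, fixed in advance, for values below detection (censoring or a named substitution).
4. A sensitivity analysis of the paired raw differences, because the error structure near the detection limit is unknown.

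State that the dose-linearity models do not apply to this study's single BaP dose, and do not replace them with an ln-on-ln slope rule. The cost is a few sentences of SAP wording. No extra subjects, samples or assays are needed. The one real piece of work is choosing the below-detection rule, which will matter more for minor metabolites and late time points than for Cmax.
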